28.	Publication Policy.....	29
29.	References	30
30.	Appendices.....	31
30.1.	Appendix A: Pigment Clearance Score Pigment Score	32
30.2.	Appendix B: Fitzpatrick Wrinkle Score (FWS)	33
30.3.	Appendix C: Subject Pain Scale	34
30.4.	Appendix D: Subject Satisfaction Scale	35
30.5.	Appendix E: Local Skin Response	36

1. Study Synopsis

Protocol Number	PWY18010
Protocol Version	v 1.0 28NOV2018
Protocol Title	Evaluation of the PicoWay® Laser System with 730 nm and Resolve™ Fusion Handpieces for Treatment of Benign Pigmented Lesions and Wrinkles
Short Title	PicoWay 730 Resolve Fusion
Device Description	PicoWay® Laser System, Candela Corporation, Wayland, MA
Study Design	Prospective, non-randomized, multi-center, evaluator blinded, safety and efficacy clinical study
Study Objective	Evaluate the safety and efficacy of the PicoWay® Laser System with 730 nm and Resolve™ Fusion handpieces for treatment of benign pigmented lesions including dyschromia, and wrinkles including fine lines
Investigative Sites	Up to two (2) investigational sites located in the United States
Number of Subjects	Up to 160 subjects
Study Duration	The overall duration of this study is not expected to exceed 24 months
Study Overview	
Upon enrollment subjects will be assigned to one or possibly both of the following laser treatment groups based on their qualifying indications:
 
Group A: Benign Pigmented Lesions including dyschromia Group B: Wrinkles including fine lines
 
Subjects will receive up to 4 laser treatments at 6 ± 2 week intervals with the PicoWay® Laser System. Handpiece selection and specific treatment parameters will be determined by the clinician.
 
The treatment area will be photographed at every visit. Baseline photographs will be compared to follow-up photographs to determine the effectiveness of the laser treatments.
 
The Study Doctor or staff will contact subjects by telephone 10 days after each treatment visit to assess healing response.
 
Optional skin punch biopsies may be collected prior to or immediately after laser treatment, or at follow-up visits at clinician's discretion.
 
Subjects must provide signed written consent prior to any biopsy procedure. Subjects may still participate in the study if they choose not to undergo biopsies.
 
Subjects will be scheduled for follow-up visits at 4 ± 1 week, 8 ± 2 weeks and 12 ± 2 weeks after the final laser treatment. Additional visits may be requested at the discretion of the clinician.

Study Population	
Adults seeking treatment of benign pigmented lesions including dyschromia and/or wrinkles including fine lines, and who satisfy all study inclusion and exclusion criteria, and who provide written informed consent will be considered eligible for this study.

Study Eligibility	
Inclusion Criteria
 
Subjects must meet all inclusion criteria to be enrolled in this study:
 
 1. Willing to provide signed informed consent 2. Adults age 21 to 80 3. Fitzpatrick Skin Type (FST) I to VI 4. Presence of benign pigmented Lesions assessed at baseline as Pigment Severity Score (PSS) of "2" or higher and/or wrinkles assessed at baseline as Fitzpatrick Wrinkle Score (FWS) of "2" or higher 5. Willing to allow photographs and/or video to be taken of treated areas for the purposes of this research study 6. Willing to abstain from any other procedures for treatment of benign pigmented lesions or wrinkles in the laser treatment areas for the duration of the study including surgery, light, laser, ultrasound or radiofrequency treatments 7. Willing to abstain from use of prescription cosmetic products for treatment of benign pigmented lesions or wrinkles in the laser treatment areas for the duration of the study including injections of neurotoxins or dermal fillers, skin lightening creams, and wrinkle creams 8. Willingness to adhere to study treatment and follow-up visit schedules 
Exclusion Criteria
 
Subjects who meet any exclusion criteria cannot be enrolled in the study:
 
 1. Pregnant, planning pregnancy or breast feeding 2. Allergy to topical or injectable lidocaine or similar medications 3. Allergy to topical steroid or similar medications 4. Unprotected sun exposure in the six weeks prior to enrollment, or active tan in the laser treatment area 5. History of melanoma in the intended treatment area 6. History of keloid or hypertrophic scar formation 7. Use of topical or systemic retinoid therapy during the past six (6) months 8. Use of neurotoxins in the intended treatment area within the past three (3) months or throughout the duration of the study 9. Use of dermal fillers in the intended treatment area within the last six (6) months or throughout the duration of the study

	
 10. Severe immunosuppression resulting from medications and/or a medical condition that could impair healing after treatment. 11. Open wound or infection in the intended treatment area 12. History of light induced seizure disorders 13. Dermatologic and/or cosmetic procedures in the intended treatment area(s) during the past six months 14. The subject is not suitable, in the opinion of the clinician, for participation in the study due to medical or other reasons that could compromise the study integrity or subject safety
Study Visit Outline	
NOTE: Screening Visit and Baseline/Treatment Visit #1 may occur on the same day
 
Screening Visit:
 
 1. Informed Consent 2. Inclusion and Exclusion Criteria Review 3. Medical History Review 4. Concomitant Medication Review 5. Fitzpatrick Skin Type (FST) Evaluation 6. Benign Pigmented Lesion and Wrinkle Evaluation 
Baseline / Treatment Visit #1:
 
 1. Clinical Photography 2. Laser Treatment 3. Local Skin Response Assessment 4. Subject Pain Score Assessment 5. Safety Assessment 6. Skin Biopsy (optional) 
Telephone Contact
 
 1. 10 days +/- 7 days after each treatment 
Treatment Visits #2 to #4:
 
 1. Clinical Photography 2. Subject Satisfaction Score 3. Laser Treatment 4. Local Skin Response Assessment 5. Subject Pain Score Assessment 6. Safety Assessment 7. Skin Biopsy (optional) 
Follow-Up Visits: 4 ± 1 week, 8 ± 2 weeks, 12 ± 4 weeks.
 
 1. Clinical Photography 2. Subject Satisfaction Score 3. Local Skin Response Assessment 4. Safety Assessment 5. Skin Biopsy (optional)
Measurement Instruments	
5-Point Pigment Clearance Scale (Appendix A)
 
9-Point Fitzpatrick Wrinkle Scale (Appendix B)

	
11-Point Subject Pain Scale (Appendix C)
 
5-Point Subject Satisfaction Scale (Appendix D)
 
Local Skin Response (Appendix E)

Primary Efficacy Endpoints	
1. Benign Pigmented Lesions Mean difference from Baseline to 12-week follow-up in Pigment Clearance Score (PCS) as determined by blinded evaluators from clinical photography
 
2. Wrinkles Mean difference from Baseline to 12-week follow-Up in Fitzpatrick Wrinkle Score (FWS) as determined by blinded evaluators from clinical photography

Secondary Efficacy Endpoints	
1. Benign Pigmented Lesions Percentage of subjects demonstrating Pigment Clearance Score (PCS) of 3 or 4 (> 50% improvement) comparing Baseline to 12-week follow-up as determined by blinded evaluators from clinical photographs
 
2. Wrinkles Percentage of subjects demonstrating ≥ 1 score improvement in Fitzpatrick Wrinkle Score (FWS) from Baseline to 12-week follow-up visit as determined by agreement of 2 out of 3 blinded evaluators from clinical photographs
 
3. Subject Satisfaction Mean and distribution of Subject Satisfaction Scores at all visits beyond Treatment Visit #1
 
4. Subject Pain Mean and distribution of Subject Pain Scores following each treatment

Primary Safety Endpoint	Incidence, severity and relatedness of adverse device effects based on total number of laser treatments performed
Exploratory Endpoint	Analysis of laser-tissue effects and/or healing response from pre- and post-treatment skin biopsies using light microscopy and/or scanning electron microscopy

2. Abbreviations

ADE	Adverse Device Effect
cm, cm²	Centimeter, Square Centimeters
CFR	Code of Federal Regulations
Ø	Diameter
FDA	Food and Drug Administration
FST	Fitzpatrick Skin Type
FWS	Fitzpatrick Wrinkle Score
GCP	Good Clinical Practice
Hz	Hertz
IEC	Independent Ethics Committee
IRB	Institutional Review Board
J	Joule
µbeam	Microbeam
µm	Micron
µs	Microsecond
mJ	Millijoule
mm	Millimeter
ms	Millisecond
nm	Nanometer
Nd:YAG	Neodymium: Yttrium Aluminum Garnet (YAG)
NSR	Non-Significant Risk
PCS	Pigment Clearance Score
PSS	Pigment Severity Score
ps	Picosecond
SE	Side Effect
SOP	Standard Operating Procedure
Tx	Treatment
UADE	Unanticipated Adverse Device Effect

3. Study Objective

The purpose of this study is to evaluate the PicoWay® Laser System with 730 nm handpiece and Resolve™ Fusion 1064 nm and 532 nm fractional handpieces for the treatment for benign pigmented lesions including dyschromia, and wrinkles including fine lines.

4. Background

The use of lasers to selectively target chromophores in the skin was first described by Anderson and Parrish in 1983¹ which led directly to the development of the first pulsed dye laser to be used in dermatology to treat vascular lesions. As laser technology advanced shorter pulse duration lasers, such as nanosecond pulse duration domain Q-switched Ruby and Nd:YAG lasers among others, were developed to safely and effectively remove tattoos and pigmented lesions using the same principles of selective photothermolysis.³⁻⁵ Further advances led to the introduction of lasers with pulse durations in the picosecond domain including the Nd:YAG at wavelengths of 532 nm, 1064 nm; and the alexandrite at 755 nm which have both been demonstrated as safe and effective for treatment of benign pigmented lesions, wrinkles, tattoo removal, and other indications.⁶⁻¹³

5. Study Design

This is a prospective, non-randomized, multi-center, evaluator blinded, safety and efficacy clinical study. Subjects will serve as their own control as the appearance of their benign pigmented lesions and/or wrinkles at baseline is compared to the appearance following laser treatment.

6. Study Overview

Subjects will participate in a Screening Visit to evaluate the presence of benign pigmented lesions including dyschromia, or wrinkles including fine lines. After evaluating all inclusion and exclusion criteria, and providing signed informed consent, subjects will be considered enrolled in the study and assigned a unique identification number that will appear on all records for that subject as the Subject ID.

Subjects will then either be scheduled for the Baseline / Treatment Visit #1 at a later date, or the Screening and Baseline / Treatment #1 Visits may be combined into the same visit.

Subjects will receive up to four (4) study laser treatments at 6 ± 2 week treatment intervals.

NOTE: Fewer than four (4) Treatment Visits may be required to reach maximum expected clinical results in some subjects. Treatments may therefore be stopped, and subject placed into the Follow-Up phase at the discretion of the Investigator.

The Study Doctor or staff will make up to three (3) attempts to contact subjects by telephone 10 days after each treatment to assess healing response.

After the final study laser treatment, subjects will be scheduled for three (3) follow-up visits at 4 ± 2 week intervals, or approximately 1, 2 and 3 months.

After successful completion of the 12 week follow-up visit, subjects will be exited from the study.

7. Study Population

Up to 160 subjects will be enrolled in this study at up to two (2) investigational sites in the United States.

The Study Population will be enrolled at the discretion of the Investigator after determining that eligible subjects have unwanted benign pigmented lesions including dyschromia on the face, scalp, neck, chest, back, arms, hands, legs or feet; or wrinkles including fine lines on the face.

[figure not shown]
Subjects will be assessed at the Screening Visit and allocated to one **or both** study sub-groups if eligible:

Group A: Benign Pigmented Lesions including dyschromia

Group B: Wrinkles including fine lines

The logic scheme used for group allocation is provided below in Figure 1.

Figure 1: Study Group Allocation Logic

All subjects must satisfy the inclusion and exclusion criteria and provide signed informed consent to be eligible for participation in the study. Subjects enrolled in the study can discontinue their participation at any time for any reason without prejudice or reduction in the quality of their medical care. The Investigator or Sponsor can terminate a subject's participation in this study at any time to protect the subject's health or if a subject fails to

follow directions that result in noncompliance with study procedures. Subjects who withdraw or are terminated from the study prior to completion may be replaced.

8. Inclusion / Exclusion Criteria

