10.2. Baseline and Treatment Visits

The following activities typically take place during each Treatment Visit.

Pregnancy Test

Women of childbearing potential will undergo a urine pregnancy test. Subjects with a positive pregnancy test will be discontinued from the study. The subject will be followed until the outcome of pregnancy is determined.

Photography

Prior to each laser treatment the treatment areas will be photographed using a high-resolution digital camera. Camera settings and other parameters such as distance, lighting, background and polarization will be recorded and reproduced at subsequent photography sessions.

Subject Satisfaction

At each treatment visit beyond Treatment #1, subjects will be asked to rate their level of satisfaction with the study treatments thus far using the Subject Satisfaction Scale provided in Appendix D.

Eye Safety

The correct eye protection must be worn during all laser treatments by the subject, the treating Investigator, and all other study personnel or observers in the room during laser operation.

Treatment Area Preparation

The intended treatment area will be cleansed with isopropyl alcohol or similar prior to treatment to ensure the treatment area is free of any makeup, creams or lotions.

Skin Biopsy (Optional)

Subjects may be asked if they will allow one or more skin punch biopsies to be performed at or near the treatment area prior to and/or immediately after treatment. Biopsies are optional and will only be performed after written consent is obtained from the subject. The Investigator will determine if biopsies are needed based on the condition being treated, location, or other factors. Performance of the biopsy typically follows these steps:

- a) Skin biopsies will be collected at or near the treatment area.
- b) Biopsy site will be cleansed with isopropanol alcohol or similar.
- c) Local anesthetic injection (lidocaine or similar medication) will be administered intradermally to the biopsy site prior to collection.
- d) Biopsy will be collected using sterile, single use disposable 2 mm to 4 mm punch biopsy.
- e) Sutures may be used to close the biopsy site as needed.
- f) Biopsies will be placed in a container labeled with Subject's ID number and date of collection.
- g) Biopsies will be fixed and processed for hematoxylin and eosin staining and/or scanning electron microscopy according to laboratory guidelines.

Anesthesia

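### Apart from subjects judged to have reached their best result, the protocol does not separate stopping laser treatment from leaving the study, so treated subjects can lose their 12-week photograph and be replaced

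*Combined protocol and SAP*

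**What the plan says.** Section 6 (Study Overview) sets the course: "Subjects will receive up to four (4) study laser treatments at 6 ± 2 week treatment intervals". A note there, repeated in Section 11 (Schedule of Events), adds: "Fewer than four (4) Treatment Visits may be required to reach maximum expected clinical results in some subjects". It continues: "Treatments may therefore be stopped, and subject placed into the Follow-Up phase at the discretion of the Investigator". The reason for stopping early is a good result, the decision is the Investigator's, and no criterion is given. The general follow-up sentence in Section 6 reads: "After the final study laser treatment, subjects will be scheduled for three (3) follow-up visits at 4 ± 2 week intervals".

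Section 7 (Study Population) covers other reasons: "The Investigator or Sponsor can terminate a subject's participation in this study at any time to protect the subject's health", or where a subject fails to "follow directions that result in noncompliance with study procedures". It then says: "Subjects who withdraw or are terminated from the study prior to completion may be replaced". Section 10.2, on pregnancy testing, says: "Subjects with a positive pregnancy test will be discontinued from the study". In each case the text speaks of the study and not of laser treatment alone.

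Table 1 in Section 11 marks study exit only at the 3-month visit and has no column for an early exit. Section 17.1 defines both primary effectiveness endpoints at the 12-week visit. Section 19.4 analyses effectiveness in a Per Protocol population and gives subjects withdrawn before the final assessment as an example of those excluded. Section 19.5 analyses safety in all treated subjects.

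**The concern.** There is no concurrent control. Group A is tested against a fixed 50% responder rate and Group B against zero mean change (Section 19.2), so no comparator arm has a similar loss to offset a selective one.

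The texts treat two kinds of early stopper differently. One judged to have done as well as expected is explicitly sent on to the follow-up photographs. For one stopped on health grounds, the only written provision is termination from the study, with possible replacement. In Group A the health ground can touch the endpoint itself: Section 10.2 names hyperpigmentation and hypopigmentation as anticipated adverse device effects, and Section 21.1 lists them among the potentially more severe or lingering responses. A subject who leaves for that reason may well have a poor pigment result.

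This is a data-collection gap as well as an analysis-set question. Moving to an all-treated analysis would not fill it, because no 12-week photograph would exist to score. Section 22.2 follows adverse effects to resolution but asks for no efficacy photograph.

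**Working it through.** **Inputs.** From Section 19.3: Group A, 30 evaluable subjects, 50% against 75%, two-sided exact binomial test at 5%; Group B, 34 evaluable subjects, 1-point change, SD 2, two-sided paired t-test at 5%. Section 7 caps enrolment at 160, against 30 + 34 = 64 evaluable, so there is room to replace subjects. The loss rates below are assumptions, because the documents give none.

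**Step 1: the plan's own figures.**
- Group A: the smallest r with P(X ≥ r | 30, 0.50) ≤ 0.025 is r = 21. The tail is 0.0214 and the two-sided p is 2 × 0.0214 = 0.043. At 20/30 the two-sided p is 0.099. Power at 75% is P(X ≥ 21 | 30, 0.75) = 80.3%.
- Group B: noncentrality (1/2) × √34 = 2.92, power 80.8%.

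Both agree with the stated 80%.

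**Step 2: selective loss with replacement, Group A.** Let p be the true responder rate, f the share of non-responders lost and g the share of responders lost. After replacement up to 30 evaluable subjects, the rate among those analysed is q = p(1 − g) / [p(1 − g) + (1 − p)(1 − f)]. With p = 0.50:

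| f | g | All subjects lost | q | P(X ≥ 21 of 30) |
|---|---|---|---|---|
| 0 | 0 | 0% | 50.0% | 2.1% |
| 10% | 10% | 10% | 0.45/0.90 = 50.0% | 2.1% |
| 10% | 0 | 5% | 0.50/0.95 = 52.6% | 4.1% |
| 20% | 0 | 10% | 0.50/0.90 = 55.6% | 7.8% |
| 30% | 0 | 15% | 0.50/0.85 = 58.8% | 14.5% |
| 20% | 5% | 12.5% | 0.475/0.875 = 54.3% | 6.0% |
| 30% | 10% | 20% | 0.45/0.80 = 56.3% | 9.0% |

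Inflation comes from the difference between f and g, not from loss as such.

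**Step 3: counting lost subjects as failures.** An observed 21/30 has p = 0.043. With one lost subject counted as a failure it is 21/31, p = 0.071; with two, 21/32, p = 0.110; with three, 21/33, p = 0.163.

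**Step 4: Group B.** Suppose the true mean change is zero and a share d, whose wrinkles are worse by m points on average, is lost. Those kept then have mean improvement dm/(1 − d). With 34 subjects and SD 2, the upper-tail error, nominally 2.5%, becomes:
- d = 5%, m = 0.5: mean 0.026, error 3.0%
- d = 10%, m = 1: mean 0.1/0.9 = 0.111, error 5.0%
- d = 20%, m = 1: mean 0.2/0.8 = 0.25, error 10.5%

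**Limit of the illustration.** Steps 2 and 3 use the responder test of Sections 19.2 and 19.3. Section 17.1 lists a mean difference as the Group A primary endpoint, and these figures do not address that.

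**The case against.** A reader might infer that every subject stopped for a reason other than maximum result is terminated and replaced. The documents do not say so. Section 7 is permissive on both counts: participation can be ended, and those who leave may be replaced. Only a positive pregnancy test requires discontinuation, and nothing links that to pigment or wrinkle response. The general follow-up sentence in Section 6 runs from the final treatment and sets no condition on why it was the last. The plan is silent on other early stoppers; it does not bar them from follow-up.

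A reader might also infer that reaching the 12-week photograph depends on outcome by design. That is not supported either. Poor response and pain are not written grounds for termination, and a poor responder can complete four treatments and the same follow-up. Nor does the maximum-result note itself create bias: it changes how many treatments the subject receives, not whether the subject is observed. Photographs are also taken before every treatment, so a subject who leaves has some images.

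These points stand, and they limit the claim to a risk. They do not remove it. Two sites could handle the same subject differently and both comply. No rule uses an earlier image for a 12-week endpoint. Replacement of treated subjects and exclusion of withdrawn subjects from efficacy are both written into the plan. The overlap with the Per Protocol exclusion is real, but correcting that exclusion alone would leave the photographs missing.

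**Conclusion.** The point holds as a gap with a possible bias of unknown size. The protocol separates stopping laser treatment from leaving the study only where maximum result is the reason. Elsewhere, its rules on termination, replacement and the Per Protocol population allow treated subjects to drop out of the efficacy result.

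The direction is towards success only if loss falls more on those with poor outcomes; if it is unrelated to response, the error rate does not change. Under the assumed one-sided losses of 10% to 30% of non-responders, the Group A false-success chance roughly doubles at the low end and rises nearly sevenfold at the high end. A result at the cut-off would not survive counting one lost subject as a failure. The plan's sample-size figures reproduce and are not in dispute.

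**What to change.** Reconcile Sections 6, 7, 10.2 and 11 so that stopping laser treatment is distinct from leaving the study:

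- State that a treated subject who stops laser treatment early, for whatever reason, stays in the existing follow-up schedule for photographs and assessments, unless the subject withdraws consent or the existing rules end participation.
- Offer a photograph at exit to those who leave.
- Allow replacement only for subjects who were never treated, so that replacement does not remove treated subjects from the efficacy denominator. Section 19.4 then needs to say how a treated subject without a 12-week score is counted.

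None of this alters when or why treatment or participation is stopped, and the pregnancy rule is unchanged. The cost is protocol wording, a few extra follow-up visits already in the schedule, and possibly a slightly less favourable responder rate. It is best done before subjects start leaving, since missed photographs cannot be recovered.
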